Official Title: Effects of Toe-out Gait Modification on Clinical and Biomechanical Measures in People with Knee Osteoarthritis

- NCT Number: NCT02019108
- **Document Date:** November 25, 2013

Methods

Participants

Community-dwelling individuals were recruited via an existing laboratory database as well as advertisements in print media. Inclusion criteria were: (i) definitive medial tibiofemoral osteophytes on x-ray; (ii) joint space narrowing greater in the medial tibiofemoral compartment compared to the lateral compartment; (iii) history of knee pain longer than six months; and (iv) average knee pain of at least 3 out of 10 over the one month period prior to initial screening. Exclusion criteria were: (i) knee surgery or intra-articular pain relief injection within six months; (ii) current or past (within six months) oral corticosteroid use; (iii) history of knee joint replacement or tibial osteotomy; (iv) any other condition affecting lower limb function; (v) participation in a new structured exercise program within the past three months, or planning to commence exercise or other treatment for knee OA in the next four months; and, (vi) an inability to travel to the university to attend testing and training sessions. The study was approved by the Institution's Clinical Research Ethics Board and all participants provided written informed consent.

Sample size was determined based on randomization with stratification, and covarying for baseline values in the statistical analysis. Using effect size estimates of 0.8 for WOMAC pain and 1.0 for KAM impulse, based on pilot data using a similar design, it was determined that participants in each group was required to attain 90% power to detect significant differences in pain and KAM outcomes between groups with an alpha of 0.05. Using a conservative estimate of 10% attrition, the aim was to recruit 73 participants for this study.

Study Design

This was a parallel group, assessor-blinded, randomized controlled trial. Interested participants were initially screened for inclusion and exclusion criteria over the telephone and eligible individuals then underwent a physical screen. Screening was overseen by a researcher not involved in data collection or analysis.

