Participants returned to the university the following week (Week 1) to begin their training program, and were informed of their group allocation at this time. Each home-based program lasted four months and was supplemented with eight training sessions with the study trainer at Weeks 1, 2, 4, 6, 8, 10, 12 and 15 of the intervention, with typical sessions lasting 20 minutes in Week 1 and increasing to 40 minutes by Week 15. All training sessions, regardless of group allocation, were conducted by the same trainer in the same rehabilitation gymnasium. The first training session for each participant was always a one-on-one session with the trainer, with subsequent sessions conducted in groups of one to three individuals; in cases of group sessions, only individuals from the same group allocation were present in the gymnasium to prevent cross-contamination of groups.

Follow-up testing occurred four months after baseline testing, with a final retention testing session conducted one month later. The same outcome measures, completed in the same testing order, and by the same blinded assessor, were collected at each testing session. No training or instructions of any kind were provided between these final two testing sessions.

Interventions

For both groups, the intent was to increase the weekly amount of walking out in the community by 40% over and above that exhibited prior to enrollment. Initial values were assessed via discussion with participants at the first training session, and prescribed weekly increases were determined individually at each training session in consultation with the trainer.

Toe-out (TO) gait modification program

Participants randomized to the TO program were trained to perform walking with 15° more toeout than the self-selected amount measured at the baseline testing session. Our previous pilot study showed modest improvements of 6.7° in self-selected toe-out angle following 10-weeks of toe-out gait retraining intending to increase toe-out by 10°, that resulted in marginally statistically significant improvements in late stance KAM (p=0.04) and self-reported pain (p=0.02), and non-significant decreases in KAM impulse (p=0.20). Thus, a larger toe-out increase was selected for this study.

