Toe-out modification during the training sessions was facilitated with mirror-guided biofeedback of performance. Participants placed their study foot on a protractor device at the target toe-out angle for that session, and verbally instructed the therapist in the placement of a piece of green tape on the mirror to best cover the reflection of the foot in this target position. The tape remained on the mirror during the training session to guide foot placement during treadmill walking. To promote motor learning, a faded feedback paradigm was used with removal of real-time biofeedback commencing at session 4 (mean percentage of walking time with feedback: Week 6 = 90%; Week 8 = 75%; Week 10 = 60%; Week 12 = 45%; Week 15 = 35%). Self-reported difficulty in achieving the target angle was recorded at each training session using an 11-point numerical rating scale (NRS) with terminal descriptors of 0 = "no difficulty" and 10 = "unable to perform"). Participants were instructed to maintain the increased toe-out angle outside the training sessions whilst walking in the community.

Progressive walking (PW) program

Participants randomized to the PW program underwent all training procedures as those in the TO group, with the exception of receiving no training or instruction related to toe-out walking. This included walking on the treadmill in front of a mirror during training sessions, but without foot placement guide tape as per the TO training protocol.

Outcome measures

Pain and physical function

At each testing session, participants completed the Western Ontario and McMaster Universities Arthritis Index (WOMAC) Likert version₂₂. Average knee pain over the previous week was also assessed using an 11-point NRS with terminal descriptors of 0 = "no pain" and 10 = "worst pain imaginable". Overall perceived change at follow-up compared to baseline was assessed using a 15-point Likert scale (-7 = "a very great deal worse" 0 = "about the same", +7 = "a very great deal better"). Finally, participants completed the timed stair climb test where they were instructed to ascend 12 stairs "as quickly as possible", and the fastest time from the two attempts was recorded.

Gait biomechanics

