Gait data were recorded for barefoot, over ground walking trials at a self-selected speed. Twentytwo retro-reflective markers were affixed to the participant according to a modified Helen Hayes marker set, and their movements were captured using twelve high-speed digital cameras (Motion Analysis Corp., Santa Rosa, CA) sampling at 100 Hz. An initial standing static trial was collected using additional markers placed over the medial malleoli and femoral epicondyles to determine segment orientations and joint centres of rotation. Kinematic data from the cameras were synchronized with two force platforms (OR6-6, Advanced Mechanical Technologies Inc.) visually concealed in the floor of a 10m walkway and sampling data at 2000 Hz. Participants were provided no instructions pertaining to walking mechanics during any of the gait assessments.

Inverse dynamics techniques and commercially available software (Orthotrak, Motion Analysis Corp.) were used to calculate gait variables including: KAM (early stance peak, late stance peak, impulse), peak external knee flexion moment (KFM) during stance, and mean foot progression angle during foot-flat (positive values = toe-in orientation, negative values = toe-out orientation). The mean value from five walking trials was calculated for each biomechanical variable.

Adherence, concurrent treatments, and adverse events during interventions

Adherence to both training programs was assessed as the total number of supervised walking sessions attended for each participant. Compliance with the prescribed walking increases was obtained from log book data completed by participants detailing their daily amount of walking for the duration of the study, and weekly totals (in hours) were calculated. Additionally, an 11-point NRS (0 = "not confident at all", 10 = "very confident") in the log book was used to assess self-reported confidence in the ability of those in the TO group to maintain the increased toe-out angle whilst walking in the community. Finally, concurrent treatments and adverse events reported during the intervention were assessed using open-ended questions in the log book maintained by the participants. For the purposes of analysis, adverse events were defined as those lasting longer than two weeks in duration, or requiring additional treatment.

Statistical analysis

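### Adverse events rest on one described source, an open-ended log book the participant keeps, with no described staff query or follow-up of those who stop, so harms may be under-counted and any between-arm comparison biased in an unknown direction

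*Combined protocol and SAP*

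**What the plan says.** The section on adherence, concurrent treatments and adverse events gives the whole harms method: harms and other treatments during the programme were recorded "using open-ended questions in the log book maintained by the participants". A counting rule follows: for analysis, "adverse events were defined as those lasting longer than two weeks in duration, or requiring additional treatment". The same book holds the walking diary, described as "log book data completed by participants detailing their daily amount of walking for the duration of the study".

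Staff contact is frequent. Under Study Design the home programme is "supplemented with eight training sessions with the study trainer at Weeks 1, 2, 4, 6, 8, 10, 12 and 15", with one trainer for both arms. The toe-out section shows that these sessions already serve to collect data: "Self-reported difficulty in achieving the target angle was recorded at each training session". Follow-up and retention testing come later and are run by a blinded assessor. No adverse event question is described at any of these contacts.

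The sample-size paragraph under Participants expects losses: "Using a conservative estimate of 10% attrition, the aim was to recruit 73 participants for this study". The Statistical analysis section assumes data missing completely at random, with multiple imputation as a sensitivity analysis. It names no adverse event comparison, denominator or rule for missing log books.

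**The concern.** The harm record depends on the participant continuing to write in the book and then handing it in. Someone who stops because walking has become painful is a plausible person to do neither. Missing harm data may therefore depend on harm.

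The counting rule adds to the problem. Deciding whether an event lasted over two weeks or needed extra treatment requires onset, end and treatment, which free text may not supply. If a participant stops writing within two weeks of onset, an untreated event cannot be shown to qualify, even if the book comes back. A blank or missing book could also be read as no event, since no rule says otherwise.

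Harms matter in this trial. Both arms aim for 40% more walking. The toe-out arm adds a 15° change, larger than the 10° pilot target, in people with painful knees. No primary outcome is affected. What is at stake is whether the trial can support a statement about tolerability.

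**Working it through.** **1. The plan's own figure.** Inputs from the sample-size paragraph: effect size 0.8 for WOMAC pain, 90% power, alpha 0.05. Two-sided testing and 1:1 allocation are assumed because neither is stated.

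- Per arm: n = 2(1.960 + 1.282)² / 0.8² = 32.8, so 33; total 66.
- With 10% attrition: 66 × 1.10 = 72.6, so 73; or 66 / 0.90 = 73.3, so 74.

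The target of 73 is reproduced by the first form of inflation. Expected loss is 0.10 × 73 = 7.3, about 7 people. Neither cause nor arm is given.

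**2. What the text covers.**

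| Element | Described? |
|---|---|
| Log book questions on adverse events | Yes, open-ended |
| Question from staff at the eight sessions | No |
| Question from staff at follow-up or retention | No |
| When log books are collected or read | No |
| Unreturned log books | No |
| Contact with people who stop | No |
| Denominator or comparison for adverse events | No |

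**3. Direction of bias.** No event counts are given, so those below are assumed. Arms of 36 (toe-out) and 37 (progressive walking) are also assumed, with all randomised as denominator. Risk difference (RD) = a/36 − b/37. Risk ratio (RR) = (a/36)/(b/37). Here a and b are the events left after the stated number of records with events is lost.

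| True events | Records lost (toe-out/walking) | Observed events | RD, points | RR |
|---|---|---|---|---|
| 8 v 4 | 0/0 | 8 v 4 | 11.4 | 2.06 |
| 8 v 4 | 4/0 | 4 v 4 | 0.3 | 1.03 |
| 8 v 4 | 4/2 | 4 v 2 | 5.7 | 2.06 |
| 8 v 4 | 2/2 | 6 v 2 | 11.3 | 3.08 |
| 8 v 4 | 0/2 | 8 v 2 | 16.8 | 4.11 |
| 8 v 4 | 7/0 | 1 v 4 | −8.0 | 0.26 |
| 8 v 8 | 0/0 | 8 v 8 | 0.6 | 1.03 |
| 8 v 8 | 4/0 | 4 v 8 | −10.5 | 0.51 |

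No row loses more than the 7 people the plan expects. A true excess can vanish, shrink on one scale only, grow or reverse, and a difference can appear where there is almost none. Taking returned log books as the denominator gives a similar pattern: for 8 v 4 with 4/0 lost, 4/32 − 4/37 = 1.7 points and RR 1.16.

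**4. A milder illustration, also assumed.** Take 36 per arm, 3 lost per arm and 3 events among 33 completers in each arm. The log books show 9% v 9%. If all three toe-out losses and none of the others followed a countable harm, the truth is 6/36 v 3/36 (17% v 8%). If one did, it is 4/36 v 3/36 (11% v 8%).

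**The case against.** A reader might infer that the comparison is biased toward no difference. The documents do not support that. It needs harm-related loss concentrated in the arm with more harm, and not so large that it reverses the difference. The documents give no attrition by arm or cause. Participants also know their allocation from Week 1, so open-ended self-report could widen a difference. This objection stands in full.

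A reader might also infer that records are in fact lost, or that staff learn of events only from the log book. Neither is stated. The text does not say when books are collected. They could be read at any session, in which case earlier entries of a later drop-out would survive. Walking increases are set in discussion with the trainer at each session. Attenders also report pain on WOMAC and a 0–10 scale, and give a rating of overall change. So loss of the record is a risk and not a documented fact, and a trainer may well hear of worsening. That does not make such talk an adverse event record: the plan describes none arising from it.

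Nor does the plan specify a harm comparison; the Statistical analysis section has only a general statement about group effects for all outcomes. Any bias therefore attaches to an analysis not yet defined. That is a further gap rather than a defence.

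Finally, the event counts above are invented, and the trial is too small to separate such rates: Fisher's exact test gives p = 0.48 for 6/36 v 3/36 and p = 1.0 for 4/36 v 3/36. This is correct, but the value of harm data here is an honest count by arm, not a significance test.

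**Conclusion.** The concern holds in a limited form. The log book is the only adverse event source described, and following the plan as written can miss harms in people who stop or do not return it. About 7 of 73 participants are expected to leave. With event counts of the order assumed above, that is enough to make a between-arm harm result uninterpretable in either direction. The size of any bias cannot be computed, because event rates, reasons for stopping and return of log books are not in the documents. The scenarios show only what is possible.

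This should be changed, although no primary outcome depends on it. It is more than missing detail, because a better method is available at contacts that already take place.

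**What to change.** In the adverse events section, make the log book a secondary source and add the following.

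- **Training sessions:** the trainer asks each participant, in private and in identical non-leading words in both arms, about new or worse symptoms and any treatment for them. Onset, end and treatment go on a site-held form. Privacy matters because later sessions may include up to three people.
- **Follow-up and retention visits:** the research coordinator asks the same question. The blinded assessor should not, because answers could reveal allocation. The plan should confirm that these are different people.
- **Participants who stop:** the coordinator makes one call to record the reason and any event to that date.
- **Log books:** state when they are collected.
- **Analysis:** report events by arm with all randomised as denominator, and report unreturned log books and withdrawal reasons by arm.

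The cost is a one-page form, a minute or two per visit and about seven calls, all by existing staff. There are two downsides. The trainer knows allocation, which fixed wording limits but does not remove, and reported event counts will rise somewhat.

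The text is in the past tense. If data collection is already over, only the last two items remain possible, and the report should state the limitation.

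### Logged adverse events of two weeks or less that needed no additional treatment are left out of the analysis in both arms, and nothing else in the plan restores them

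*Combined protocol and SAP*

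**What the plan says.** The section on adherence, concurrent treatments and adverse events states that "adverse events reported during the intervention were assessed using open-ended questions in the log book maintained by the participants". It sets no minimum duration or severity for an entry. The next sentence narrows what is analysed; for that purpose, "adverse events were defined as those lasting longer than two weeks in duration, or requiring additional treatment".

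The Statistical analysis section does not mention adverse events. It names three primary outcomes (WOMAC pain, KAM impulse and foot progression angle) and treats all other biomechanical and clinical outcomes as secondary. No adverse event table, severity grading, separate count of falls or listing of all logged events is described anywhere.

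On exposure, Study Design says "Each home-based program lasted four months and was supplemented with eight training sessions with the study trainer". Under Interventions, the toe-out arm was "trained to perform walking with 15° more toeout than the self-selected amount measured at the baseline testing session", and for both arms "the intent was to increase the weekly amount of walking out in the community by 40% over and above that exhibited prior to enrollment".

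**The concern.** The rule acts after the data are collected. Participants may record any event, and the analysis then discards a class of them by definition. In people with painful knees who are asked to walk more, and in one arm to walk differently, short-lived musculoskeletal complaints are a plausible cost of the programme. A reader deciding whether the training is tolerable would want to see them.

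What is at stake is the harms statement, not the efficacy result. If the report says that few adverse events occurred, that count describes only persistent or treated events, while the log books may hold others that were never summarised.

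**Working it through.** The plan gives no adverse event rate or count to reproduce, and the recruitment target of 73 does not enter this point. The check is mainly one of logic.

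**1. What the rule excludes.** Counted: duration over two weeks OR additional treatment required. The complement is duration of two weeks or less AND no additional treatment.

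| | Untreated | Additional treatment |
|---|---|---|
| Two weeks or less | not counted | counted |
| Longer than two weeks | counted | counted |

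One cell of four is lost. A short flare or fall that needed treatment is kept, and so is an untreated fall whose effects last beyond two weeks.

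**2. How the threshold sits against the training schedule.** Study Design puts sessions at Weeks 1, 2, 4, 6, 8, 10, 12 and 15. The gaps are 1, 2, 2, 2, 2, 2 and 3 weeks, so six of the seven are two weeks or less. Walking increases were set individually at each session, and the toe-out target was specific to the session. In six of the seven intervals, an untreated complaint that began after one session and settled by the next would not be counted.

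**3. Whether another measure fills the gap.** WOMAC, the knee-pain rating and the stair climb are taken at testing sessions only: baseline, four months, and one month after that. The knee-pain rating asks about the previous week. Four months is 4 × 52/12 = 17.3 weeks, so the follow-up rating looks back over about 1/17.3 = 5.8% of the programme, and only at the knee. The perceived-change scale compares follow-up with baseline as a whole. None of these can show a flare in mid-programme that resolved, an untreated fall, or a hip or ankle complaint recorded as an event.

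**4. How much is lost.** This cannot be computed from the documents. To show how strongly it depends on unknowns, assume exponentially distributed durations and a treated share that is independent of duration. Neither assumption comes from the plan. Then

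share counted = 1 − (1 − exp(−14/mean days)) × (1 − treated share)

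| Assumed mean duration | 0% treated | 10% treated | 30% treated |
|---|---|---|---|
| 3 days | 0.9% | 10.8% | 30.7% |
| 7 days | 13.5% | 22.2% | 39.5% |
| 14 days | 36.8% | 43.1% | 55.8% |
| 28 days | 60.7% | 64.6% | 72.5% |

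For example, with a mean of 7 days and 30% treated: 1 − (1 − 0.135) × 0.70 = 0.395. The result depends almost wholly on the assumed duration and treated share, so the table is a range and not an estimate. It says nothing about differences between arms.

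**The case against.** The strongest defence is that the threshold is a deliberate and openly stated choice. Participants enter with more than six months of knee pain, averaging at least 3 out of 10. Open-ended diary questions in such people will collect ordinary symptom fluctuation, and a duration-or-treatment rule separates events from noise. The excluded class is likely the mildest. The rule is the same in both arms, no formal safety test is specified, and nothing forbids a descriptive listing of the other entries.

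Much of this stands. It justifies a labelled subset of persistent or treated events. It does not justify making that subset the only thing analysed, because the plan provides no other place where the remaining entries would appear.

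The defence also rules out some stronger readings:

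- A reader might infer that the rule removes more events from the toe-out arm and so biases the comparison towards no difference. The documents do not show this. The progressive walking arm has the same procedures apart from toe-out instruction, and both arms aim for the same increase in walking, so both share a plausible source of short complaints. A toe-out excess is a reasonable clinical conjecture, but no event rate is given for either arm.
- A reader might infer that all short flares, strains and falls are missed. Those that needed additional treatment are counted.
- A reader might try to size the effect by assuming a rate of short untreated events in each arm. Any such contrast presupposes the excess it is meant to measure. An upper confidence limit for persistent or treated events also cannot be set against a rate of short untreated ones, because they are different quantities.
- A reader might infer that harms in the month before retention testing are also lost, since the adverse event wording covers events "concurrent treatments and adverse events reported during the intervention were assessed using open-ended questions", with the follow-up session and then "with a final retention testing session conducted one month later". The log book is said to record walking for the whole study, so whether events were also recorded in that month is unclear. That is a separate ambiguity, and this point does not rest on it.

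**Conclusion.** The point holds in a limited form. By a stated rule, logged events that were both short (two weeks or less) and untreated are left out of the analysis in both arms, and no other part of the plan brings them back. If any such events were logged, absolute harm is under-counted, and any between-arm difference confined to them would go unseen. Neither the number lost nor the direction of any effect on the comparison can be derived from the documents. The range of about 1% to about 72% counted rests entirely on assumed durations and treated shares.

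The conclusion assumes that the definition is applied as written and that no unlisted summary of the other log-book entries was planned. It does not need the two arms to differ. The primary outcomes and their analyses are not affected.

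**What to change.** Add a sentence to the Statistical analysis section, and one table, summarising all log-book adverse events by arm: participants with at least one event, number of events, body site, duration, and whether additional treatment was needed. Keep the present definition (longer than two weeks, or requiring additional treatment) as a labelled subset of that table.

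This uses entries the log books were designed to collect. Where an open-ended answer does not give site or duration, report that item as not recorded. The cost is some coding of free text and a longer table that will include minor events and ordinary symptom fluctuation. The labelled subset lets the reader tell these apart from the persistent or treated events.

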This physical screen was conducted to confirm the presence of knee pain, and to perform a preliminary walking assessment to assess self-selected foot progression angle. Participants performed three trials of self-selected, over ground walking while three reflective skin markers tracked the movement of the sacrum, the second toe, and posterior calcaneus of the study limb (defined as the self-declared osteoarthritic limb in those with unilateral symptoms, or the most painful limb in the case of bilateral symptoms). The mean foot progression angle across the three trials was calculated. As the goal of the toe-out modification program was to increase the self-selected, baseline foot progression angle by 15° in the toe-out direction, 15° of toe-out at the physical screening was selected as the threshold. This was done due to (i) the difficulty in achieving toe-out angles of 30° by people with knee OA, and (ii) the fact that those who already exhibit large amounts of toe-out would likely not be candidates for toe-out gait modification in the clinical setting.

Those who passed physical screening were referred for radiographic evaluation. Standing, semiflexed, postero-anterior radiographs were obtained and graded for disease severity using the Kellgren and Lawrence (KL) OA classification system.

Individuals who met the radiographic criteria listed above were invited to the laboratory for a baseline (Week 0) testing session where self-report questionnaire, objective physical function, and biomechanical data were collected. Following completion of baseline testing, the randomization procedure was conducted by a study biostatistician who was not involved in any aspect of data collection or training. Randomization was initiated by the study research coordinator, who provided the biostatistician with each participant's study ID, sex, and KL grade. The biostatistician then responded via email with the group allocation, and maintained the randomization parameters and list offsite. Group allocations were determined prior to study commencement, and randomization was stratified by sex (male, female) and disease severity (mild or moderate grouped together, severe).

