The primary outcomes were WOMAC pain, KAM impulse, and foot progression angle, and the primary endpoint was the follow-up assessment. All other biomechanical and clinical outcomes were considered secondary in nature. Between-group comparisons were the primary analyses, with within-group comparisons used for informational purposes. Analysis of covariance (ANCOVA) models were fit predicting each outcome variable evaluated at both time points (follow-up and retention), with group as predictor, and while controlling for baseline values. For biomechanical outcomes (knee adduction and flexion moments, as well as foot progression angle), additional models were computed while additionally controlling for concurrent gait speed at the associated time point (follow-up or retention). For baseline data, crude means were computed. Adjusted least squares means (LS means) with standard errors and 95% confidence intervals were computed for each group at both follow-up and retention. Adjusted LS means were computed in similar models for within-group (delta) scores. Finally, model-adjusted group effects were computed, along with p-values and 95% confidence intervals, for all outcomes.

All data were analyzed using an intention-to-treat analysis, and the primary analyses assumed that data were missing completely at random (MCAR). In sensitivity analyses, multiple imputation was performed as per the methods described by van Buuren. Results and conclusions were compared to the MCAR analysis, and any differences noted. All statistical analyses were conducted by a biostatistician blinded to group allocation and who was not involved in any other aspect of the study. Analyses were performed using SAS v9.4 (SAS Institute, Cary, North Carolina).

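### The ANCOVA leaves out the stratification factors, sex and severity: if they are prognostic, some power is forgone and, if strata were balanced, standard errors are modestly conservative

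*Combined protocol and SAP*

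**What the plan says.** The Study Design section of the combined protocol and SAP states that "randomization was stratified by sex (male, female) and disease severity (mild or moderate grouped together, severe"), which gives four strata. On how the list was built it says only that "Group allocations were determined prior to study commencement". No blocking or other restriction within strata is described.

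The Statistical analysis section fits an ANCOVA for each outcome at follow-up and at retention, "with group as predictor, and while controlling for baseline values". One further covariate appears, for the biomechanical outcomes only: "additional models were computed while additionally controlling for concurrent gait speed at the associated time point (follow-up or retention"). No model names sex or severity.

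The Participants section ties the design to stratification but names one analysis covariate: "Sample size was determined based on randomization with stratification, and covarying for baseline values in the statistical analysis". The planning values are "effect size estimates of 0.8 for WOMAC pain and 1.0 for KAM impulse", with 90% power, alpha 0.05, 10% attrition and a recruitment target of 73.

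**The concern.** Stratifying the randomisation on a prognostic factor makes the arms more alike on that factor, so the treatment estimate varies less from one hypothetical repetition of the trial to the next. An analysis that omits the factor does not see this. It leaves the factor's variance in the residual and reports a standard error as if the balance had arisen by chance.

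Two conditions are needed. First, sex or severity must predict the outcome after its own baseline value has been taken into account. Second, allocation must be balanced within strata, for example by blocking. If both hold, intervals are too wide and tests conservative, for all three primary outcomes and for every other outcome analysed this way. If only the first holds, the reported standard error is right, but the usual precision gain from a prognostic covariate is lost.

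What is at stake is efficiency. The estimate is unbiased either way, and the error runs in the conservative direction.

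**Working it through.** **1. The plan's own figure.** Inputs from the Participants section: effect size 0.8, power 90%, alpha 0.05 (two-sided assumed), attrition 10%. Equal allocation is assumed. The per-group number is missing from the text available.

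n per arm = 2 × (1.960 + 1.282)² / 0.8² = 32.8, so 33 per arm and 66 in total. Then 66 × 1.10 = 72.6, which rounds up to 73. (Dividing instead, 66 / 0.90 = 73.3, which rounds up to 74.) The target of 73 reproduces with no stratum term.

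**2. The analytic limit.** Let R² be the share of baseline-adjusted outcome variance explained by sex and severity. The documents give no value, so 0 to 0.20 is shown. Take the baseline-adjusted residual SD as 1. The model as written reports an SE near √(2/33) = 0.246 whatever R² is. Under perfect balance within strata the true SD of the estimate is √(2(1 − R²)/33). The SE is therefore overstated by at most 1/√(1 − R²):

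- R² = 0.05: 1.026
- R² = 0.10: 1.054
- R² = 0.20: 1.118

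**3. Simulation with blocking.** Settings: 40,000 trials per row, 73 randomised, 66 analysed after random loss. Assumptions: blocks of 4 within the four strata, sex 50/50, 35% severe, R² split equally between the two factors. The model with group and baseline is compared with the same model plus sex and severity.

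| R² | Mean SE / true SD, without factors | SE too large by | Type I error, without v with | Power at 0.8, without v with |
|---|---|---|---|---|
| 0 | 0.2475 / 0.2494 | none | 5.2% v 5.1% | 88.5% v 88.4% |
| 0.05 | 0.2476 / 0.2428 | 2% | 4.5% v 4.8% | 89.0% v 90.0% |
| 0.10 | 0.2477 / 0.2382 | 4% | 4.1% v 5.1% | 89.7% v 91.6% |
| 0.20 | 0.2478 / 0.2271 | 9% | 3.2% v 4.9% | 90.7% v 94.2% |

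The mean 95% interval without the factors is 1.023, 1.052 and 1.115 times as wide as with them at R² = 0.05, 0.10 and 0.20, and its coverage is 95.5%, 96.0% and 96.8%. With the factors, the true SD of the estimate is 0.2423, 0.2366 and 0.2234, close to the values without them. The estimate therefore keeps its precision, and what is overstated is mainly the reported uncertainty. At an effect size of 1.0 (KAM impulse) the gain is under 1 point: 98.2% v 98.7% at R² = 0.10.

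**4. Simulation without blocking.** The ratio of mean SE to true SD without the factors is 0.994 to 0.998, and type I error is 4.9% to 5.1%, so the reported SE is correct. Power at 0.8, without v with the factors:

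- R² = 0: 88.2% v 87.0%
- R² = 0.05: 88.2% v 88.7%
- R² = 0.10: 88.3% v 90.4%
- R² = 0.20: 88.3% v 93.2%

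**5. Independent check.** A second simulation, with 66 completers blocked directly and 30% severe, gave an SE 3%, 5% and 11% too large at R² = 0.05, 0.10 and 0.20. Type I error was 4.3%, 3.8% and 2.9% without the factors, against 4.9%, 4.8% and 4.8% with them. The slightly larger excess is expected, because no dropout disturbs the balance there.

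**The case against.** The facts and the arithmetic are not in dispute. The case against concerns weight and support.

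- **Both conditions are unverified.** No blocking is described, and no figure is given for prognostic strength. The outcome's own baseline is already in the model and may absorb much of what sex and severity would explain, which favours a low R². This stands: the larger rows of the table have no support in the documents.
- **Adjustment can lose power.** If the list is unblocked and the factors are not prognostic, power falls from 88.2% to 87.0%. A further run of 8,000 trials per setting put the unblocked break-even near R² = 0.03 to 0.05 (87.8% v 87.7% at 0.03; 88.2% v 88.7% at 0.05). This stands, and it bounds the cost at about 1 point.
- **The scale of the effect size is not stated.** The figures above treat 0.8 as already relative to the baseline-adjusted SD. If it is relative to the raw SD, baseline adjustment alone raises power. With an assumed baseline correlation of 0.5 and R² = 0.10, simulated power is 96.4% without v 97.2% with the factors. The power gain shrinks to about 1 point, but under blocking the reported SE is still about 5% too large.
- **Evidence is uneven across outcomes.** The gain for KAM impulse is under 1 point, and no effect size is given for foot progression angle, so no power can be computed for it. The SE overstatement, however, does not depend on the effect size.
- **No fault is shown in the imputation.** The plan says "In sensitivity analyses, multiple imputation was performed" by a cited method and does not list the variables. Including the factors there follows from changing the analysis model; it does not correct a known error.

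One could also argue that controlling for baseline values was meant to cover sex and KL grade. The natural reading is each outcome's own baseline, since gait speed is named explicitly when it is added. If the wider reading was intended, one sentence would settle it.

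**Conclusion.** The concern holds in its conditional form. The analysis model does not use the factors on which the trial was randomised. If they are prognostic beyond baseline, some power is forgone; if strata were also balanced, reported standard errors are too large. For R² between 0.05 and 0.20 with blocks of 4, the excess is 2% to 9% and the power forgone at an effect size of 0.8 is 1.0 to 3.5 points. Without blocking the SE is correct and 0.5 to 4.9 points are forgone over the same range. At R² = 0 nothing is lost.

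These sizes rest on assumed R², strata shares, block size and equal allocation, and on 0.8 being on the baseline-adjusted scale. The trial's validity is not threatened, and neither the planned 90% power nor the target of 73 is undermined. It is a cheap efficiency improvement worth making in a trial of about 66 completers.

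**What to change.** Add sex and severity stratum (mild or moderate versus severe) as fixed covariates in every ANCOVA, at follow-up and retention, alongside group and the baseline value. Put the same terms in the imputation model so that it matches the analysis model. State whether the allocation list was blocked within strata. If the primary model can no longer be changed, report the adjusted model as a sensitivity analysis.

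The cost is two degrees of freedom: with 66 completers, 66 − 3 = 63 becomes 66 − 5 = 61. No new data are needed, because sex and KL grade are recorded before randomisation. Both can be given to the analyst, described as "a biostatistician blinded to group allocation and who was not involved in any other aspect of the study", without revealing allocation. The worst case is about 1 point of power, if the list is unblocked and neither factor is prognostic.
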